2. STUDY SYNOPSIS

Artemisinin Combination Therapies (ACT) are the first-line treatment for uncomplicated *Plasmodium falciparum* malaria. ACTs rapidly clear asexual *P. falciparum* parasites, responsible for clinical symptoms, but have limited activity against mature gametocytes, which are the only life stages capable of transmitting to mosquitoes. To reduce *P. falciparum* transmission, the World Health Organisation (WHO) recommends the addition of a single low dose of primaquine (0.25 mg/kg), a potent and fast-acting gametocytocidal drug, to ACT [1]. Although Artesunate-Amodiaquine (ASAQ) is a commonly used ACT, limited available data

suggest poor activity against gametocytes [2] and the added benefit of SLD PQ in combination with ASAQ remains unknown. We previously showed that Artemether-Lumefantrine (AL) is a more potent ACT in terms of gametocyte clearance and transmission reduction efficacy compared to Dihydroartemisinin-Piperaquine (DP) [3], [4] [NECTAR3, in preparation]. Recently, triple artemisinin-based combination therapies (TACT) such as Artemether-Lumefantrine plus Amodiaquine (ALAQ) have been proposed to delay the emergence of drug resistance and to provide efficacious treatment for multi-drug resistance *P. falciparum* infections [5], [6]. The transmission reducing efficacy of ALAQ or ALAQ-PQ has not yet been tested.

In this study we aim to determine transmission reducing efficacy of Artesunate-Amodiaquine (ASAQ) with and without a single low dose (0.25mg/kg) of Primaquine (SLD PQ) and Artemether-Lumefantrine (AL) with and without Amodiaquine (AQ) and Primaquine (PQ). To achieve this, we propose to conduct a five-arm, single-blind, randomised control trial to test the gametocytocidal and transmission-blocking efficacy of SLD PQ in combination with Artesunate-Amodiaquine and Artemether-Lumefantrine-Amodiaquine. Individuals will be recruited to an AL-only arm as an internal control for the ALAQ arm, and for comparison to recent trials at the same site [NECTAR3, in preparation]. Individuals who meet inclusion criteria will be randomised in a 1:1:1:1:1 ratio to: ASAQ, ASAQ-PQ, AL, ALAQ, ALAQ-PQ.

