4.2. Secondary specific objectives

- To assess differences in other mosquito infectivity parameters (mosquito infection rate, change in infection rate, infectivity to mosquitoes, and oocyst density) following treatment with ASAQ, ASAQ-PQ, AL, ALAQ and ALAQ-PQ in children and adults at all feeding timepoints compared to pre-treatment (day 0) and between treatment matched arms (ASAQ vs ASAQ-PQ, AL vs ALAQ, ALAQ vs ALAQ-PQ).
- To assess differences in gametocyte parameters (prevalence, density, circulation time, area-under-the-curve, sex-ratio) following treatment with ASAQ, ASAQ-PQ, AL, ALAQ and ALAQ-PQ in children and adults at all feeding timepoints compared to pre-treatment (day 0) and between treatment matched arms (ASAQ vs ASAQ-PQ, AL vs ALAQ, ALAQ vs ALAQ-PQ).
- To assess differences in safety parameters (AE frequency, Hb density, median drop in Hb) following treatment with ASAQ, ASAQ-PQ, AL, ALAQ and ALAQ-PQ in children and adults at all feeding timepoints compared to pre-treatment (day 0) and between treatment matched arms (ASAQ vs ASAQ-PQ, AL vs ALAQ, ALAQ vs ALAQ-PQ).
- To assess differences in biochemical parameters (ALT, CBC, Creatinine) following treatment with ASAQ, ASAQ-PQ, AL, ALAQ and ALAQ-PQ in children and adults at all feeding timepoints compared to pre-treatment (day 0) and between treatment matched arms (ASAQ vs ASAQ-PQ, AL vs ALAQ, ALAQ vs ALAQ-PQ).

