7.2. Secondary outcome measures

- Median within person percent change (presented as percent reduction) in mosquito infection rate from baseline to all feeding time-points, with comparison within and between arms.
- Median mosquito infection rate at all feeding time-points, with comparison within treatment arms compared to baseline, and between arms.
- Infectivity to mosquitoes at all feeding time-points, with comparison within treatment arms compared to baseline, and between arms.
- Mean oocyst intensity (in all/all infected mosquitoes) at all feeding time-points, with comparison within treatment arms compared to baseline, and between arms.
- Male and female gametocyte prevalence at all time-points, determined by microscopy or molecular assays, with comparison within treatment arms compared to baseline, and between arms.
- Male and female gametocyte density at all time-points, determined by microscopy or molecular assays, with comparison within treatment arms compared to baseline, and between arms.
- Male and female gametocyte sex ratio (proportion male) at all time-points, determined by microscopy or molecular assays, with comparison within treatment arms compared to baseline, and between arms.
- Gametocyte circulation time (cumulative), determined by microscopy or molecular assays, compared between treatment arms.
- Gametocyte area under the curve (cumulative), determined by microscopy or molecular assays, compared between treatment arms.
- Asexual and total parasite prevalence at all time-points, determined by microscopy or molecular assays, with comparison within treatment arms compared to baseline, and between arms.
- Asexual and total parasite density at all time-points, determined by microscopy or molecular assays, with comparison within treatment arms compared to baseline, and between arms.
- Haemoglobin density at all time-points, with comparison within treatment arms compared to baseline, and between arms.
- Median within person percent change (presented as percent reduction) in haemoglobin density from baseline to all time-points, with comparison within and between arms.
- The frequency and prevalence of adverse events (all AE's, treatment related AE's, and haematological AE's) observed up to and including day 2, 7, and 14 post-treatment, and at all timepoints.

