11.1. Analysis plan

Mosquito infectivity will be assessed at three levels: the mean number of oocysts in a sample of mosquitoes (i.e. oocyst intensity), the proportion of mosquitoes infected with any number of oocysts (i.e. mosquito infection rate), and the infectivity of the study participant to any number of mosquitoes (i.e. infectivity to mosquitoes). The primary outcome measure will be the percent change in mosquito infection rate within each arm by day 2 compared to baseline, with other time-points of infectivity assessments as secondary outcomes. Percent change will be reported as percent reduction (with 100% as total reduction of transmission, and negative values as enhanced transmission). Other secondary transmission outcomes are as described in the 'Objectives' section above. Some exploratory objectives may be published separately from the main primary/secondary outcomes.

Statistical analysis will be conducted using the most recent STATA and SAS versions (16.0 and SAS version 9.4 at time of writing). Mosquito infection data will be analysed at time-points after baseline only for those individuals who are infectious at baseline, although the data and analyses from all enrolled individuals will be published in the appendix for completeness. Individuals will be classified as infectious to mosquitoes if they infect at least 1 mosquito, with any number of oocysts. Infectivity to mosquitoes and parasite/gametocyte prevalence will be compared within and between treatment arms using generalised linear models (family: binomial, z-score, co-efficient with 95% CI) or fishers exact tests. Absolute haemoglobin density and percent change in haemoglobin density (relative to baseline) will be compared using paired t-tests (t-score for difference compared to day 0) and two-way t-tests (t-score for difference between ACT matched treatment groups at each time-point). The proportion of gametocytes that are male will be calculated for all values with total gametocyte densities of 0.2/ μ L and over. Gametocyte circulation time will be calculated to determine the average period (in days) that a mature gametocyte circulates in the blood prior to clearance, using a deterministic compartmental model that assumes a constant rate of clearance and has a

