random effect to account for repeated measures on individuals, as described previously [29]; circulation time will be analysed using t-tests (t score for difference between ACT matched treatment groups) or linear regression analyses. Area under the curve (AUC) of gametocyte density per participant over time will be calculated using the linear trapezoid method [30] using the first 28 days of observation only, and analysed by fitting linear regression models to the log10 adjusted AUC values, with and without adjustment for baseline gametocyte density (t-score, coefficient with 95% CI). All other analyses of quantitative data will be performed using Wilcoxon sign rank tests (z-score for difference compared to matched values at day 0) and Wilcoxon rank-sum tests (z-score for difference between ACT matched treatment arms at each time-point). The nonparametric van Elteren's test, an extension of the Wilcoxon rank sum test, will be used to compare the infectivity between treatment arms after adjusting for gametocyte density, as previously described [19]. This will compare infectivity between groups after stratifying into categories based on total gametocytes per microliter. Within these bins differences in infectivity between arms will be tested, thereby investigating sterilizing effects of gametocytocidal drugs. For all analyses, the threshold for statistical significance will be set at $p < 0.05$.

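### No between-arm analysis of mosquito infection adjusts for the baseline feed as a covariate, although the trial was sized with a model that could do so

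*Protocol*

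**What the plan says.** The reason for the trial is comparative: the synopsis says that "the added benefit of SLD PQ in combination with ASAQ remains unknown", and AL is included as an internal control for ALAQ. The primary outcome is not comparative: "The primary outcome measure will be the percent change in mosquito infection rate within each arm by day 2 compared to baseline". The randomised contrasts are secondary objectives (section 4.2): "between treatment matched arms (ASAQ vs ASAQ-PQ, AL vs ALAQ, ALAQ vs ALAQ-PQ".

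For quantitative outcomes with no other named test, section 11.1 prescribes "Wilcoxon rank-sum tests (z-score for difference between ACT matched treatment arms at each time-point". In section 7.2 this falls on two versions of the infection outcome:

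- the raw rate: "Median mosquito infection rate at all feeding time-points, with comparison within treatment arms compared to baseline, and between arms";
- the within-person percent change "in mosquito infection rate from baseline to all feeding time-points, with comparison within and between arms".

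It also covers oocyst intensity and gametocyte density at each visit. Post-baseline infection data "will be analysed at time-points after baseline only for those individuals who are infectious at baseline", with results for everyone enrolled placed in an appendix. Infectivity as yes or no gets a binomial GLM or Fisher's exact test, with no covariate named. A van Elteren test "will be used to compare the infectivity between treatment arms after adjusting for gametocyte density"; its strata are gametocyte density, not the baseline feed. Gametocyte AUC is regressed with and without baseline gametocyte density. The mixed-effects logistic model used for sizing in section 5.4 does not appear in section 11.1.

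**The concern.** Only the ACT-matched comparisons show what PQ adds to ASAQ or ALAQ, or what AQ adds to AL. With 20 per arm and the large between-person variation that section 5.4 assumes, much depends on whether the analysis uses what day 0 already tells us about each participant.

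The two infection-rate tests use it differently. The raw-rate test discards it. The percent-change test uses it, but as a denominator. A move from 1/50 to 3/50 infected mosquitoes scores 1 − 3/1 = −200%, while a move from 40/50 to 42/50 scores 1 − 42/40 = −5%. At 0/50 there is no score at all. The protocol does not say which test leads, so two tests with different power could disagree.

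The plan already adjusts gametocyte AUC for its baseline and reports a coefficient with a 95% CI. The infection rate, the trial's main interest, gets a z-score.

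**Working it through.** **Inputs from section 5.4:** 20 participants per arm, 50 mosquitoes per feed, 17% baseline infectivity for the average participant, ICC 0.5. On the logit scale ICC = σ²/(σ² + π²/3), so σ² = π²/3 = 3.29 and σ = 1.81. Section 11.1 gives a significance level of 0.05, taken here as two-sided.

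**Assumed, because the protocol gives neither:** the between-arm effects, and the between-visit SD (0, 1.0 or 1.8 logit, added at day 2).

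**The plan's own figure.** Section 5.4 states 88% power for the within-arm test of a 90% reduction against 80%, one-sided 0.025. Simulating a random-intercept logistic model gave 86.3% (probability scale) and 86.9% (odds scale) when 17% is read as the population mean. Read literally as the average participant's value, it gave 96–99% (probability scale) or 82–96% (odds scale). With only 100 simulations behind it, 88% carries a Monte Carlo interval of about 80–94%. Both readings are carried below. No power is stated for any between-arm comparison.

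**Hand check of the raw-rate test, 50% vs 80% reduction.** The average participant's day-2 rates are 0.17 × 0.5 = 0.085 and 0.17 × 0.2 = 0.034. Their logits are −2.376 and −3.347, a difference of 0.97. In between-person SDs this is 0.97/1.81 = 0.535. The noncentrality is 0.535 × √(20/2) = 1.69, and power is P(Z > 1.96 − 1.69) ≈ 39%. Mosquito sampling noise and loss of zero-baseline participants push it lower; the simulation gives 34%.

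**Simulation.** Two arms of 20, reductions set for the average participant and applied as a constant logit shift, baseline-infectious participants only, 1,500 runs (Monte Carlo SE at most √(0.25/1500) = 1.3 points). Adjusted means ANCOVA of the day-2 empirical logit on the day-0 empirical logit. Power in %, gains in points:

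| 17% read as | Reductions | Visit SD | Raw rate, rank-sum | % change, rank-sum | Adjusted | Gain over raw | Gain over % change |
|---|---|---|---|---|---|---|---|
| average participant | 50 vs 80 | 0 | 33.5 | 80.8 | 93.3 | 59.8 | 12.5 |
| | | 1.0 | 25.8 | 48.3 | 57.9 | 32.1 | 9.6 |
| | | 1.8 | 18.1 | 24.4 | 26.8 | 8.7 | 2.4 |
| | 80 vs 95 | 0 | 51.5 | 78.8 | 96.1 | 44.6 | 17.3 |
| | | 1.0 | 42.7 | 59.7 | 75.5 | 32.8 | 15.8 |
| | | 1.8 | 29.9 | 35.9 | 43.7 | 13.8 | 7.8 |
| population mean | 50 vs 80 | 0 | 28.4 | 64.7 | 79.9 | 51.5 | 15.2 |
| | | 1.0 | 22.9 | 35.9 | 44.7 | 21.8 | 8.8 |
| | | 1.8 | 14.9 | 19.9 | 21.7 | 6.8 | 1.8 |
| | 80 vs 95 | 0 | 44.8 | 61.3 | 84.8 | 40.0 | 23.5 |
| | | 1.0 | 36.3 | 48.6 | 64.1 | 27.8 | 15.5 |
| | | 1.8 | 26.4 | 31.3 | 36.8 | 10.4 | 5.5 |

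Type I error was 4–6% for every method.

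**All randomised participants.** For 50% vs 80%, separate runs of the adjusted analysis on all 40 gave 87–89% with no visit noise, against 93% above. The gain therefore comes from the covariate, not from adding the zero-baseline participants. Those are about 9% of participants (literal reading).

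**Rank-ANCOVA** on the baseline-infectious set, 50% vs 80%, literal reading: 87.8%, 52.3% and 24.9% for visit SD 0, 1.0 and 1.8. This is 7.0, 4.0 and 0.5 points above percent change.

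**Very large effects.** With reductions applied to the probability and visit SD up to 1.0, contrasts such as 0% vs 90% or 50% vs 99% gave at least 99% for all three methods.

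**The case against.** A reader might infer that the randomised comparisons all ignore the baseline feed and so lose much of the available power. The document does not support that. The first outcome in section 7.2 is percent change from each person's own day-0 feed, compared between arms. Against that planned test the gain is modest; the large figures apply only to the raw-rate test.

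Other points that stand:

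- The effects are assumed. The background reports effective blocking within 48 hours when PQ was added to other ACTs, and cites a feeding study in which transmission rose after ASAQ. If the PQ contrasts are that large, every method succeeds. Moderate contrasts matter more for AL vs ALAQ.
- The scale matters. With reductions applied to the probability, 50% vs 80% gives about 55%, 91% and 95% with no visit noise.
- The ICC of 0.5 describes mosquitoes from one participant. It does not separate stable differences between people from variation between visits, so it does not show how much the day-0 feed predicts.
- Zero-baseline participants are not lost from the report, and selecting on a pre-treatment value does not bias the comparison.
- The rank-sum tests are valid.

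It can also be said that covariates belong in an SAP. That carries less weight here, because section 11.1 does not leave the test open: it names one.

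**Conclusion.** The point holds as one of efficiency and specification, not validity. No between-arm analysis of mosquito infection uses the baseline feed as a covariate. The raw-rate test discards it; the percent-change test uses it imperfectly.

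For moderate contrasts, adjustment gains roughly 15 to 60 points over the raw rate and about 4 to 17 over percent change. Individual scenarios fall outside these ranges: at a visit SD of 1.8, as large as the between-person SD, the gains drop to 7–14 and 2–8 points, and one low-baseline scenario reaches 23.5 over percent change. Adjustment was ahead in every tabulated scenario. Its size rests on the assumed effects, effect scale and visit variance.

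**What to change.** In section 11.1, for the three contrasts already named in section 4.2, make the lead day-2 between-arm analysis of mosquito infection rate a baseline-adjusted one on all randomised participants. Two forms would serve:

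- the section 5.4 mixed-effects logistic model, with arm by day terms and day 0 as a repeated measure. It should include a participant-by-visit random term; otherwise mosquitoes from one feed are treated as more independent than they may be;
- ANCOVA or rank-ANCOVA of the day-2 result on the day-0 feed, with one value per participant.

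Report an effect estimate with a 95% CI. If a PQ arm infects no mosquitoes at day 2, a logistic odds ratio cannot be estimated, so state the fallback in advance. Treat log10 gametocyte density in the same way, with baseline density as covariate. Keep the rank-sum tests as sensitivity analyses.

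The cost is wording only: no new visits, samples or participants. The downside is a modelling assumption. Rank-ANCOVA largely avoids it but gives up part of the gain, and its effect estimate must be specified separately. Using all randomised participants keeps the groups whole and needs no rule for a zero denominator; it should not be presented as a further gain in power.

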11.2. Publication/Dissemination

Findings will be analysed and presented to local researchers and stakeholders in Mali and at other research meetings and symposium. Data will be submitted for publication in peer reviewed journals in due course. Anonymized data will be shared in public repositories upon publication.

12. ETHICAL CONSIDERATIONS

This research will be conducted in compliance with the protocol, Good Clinical Practice (GCP) guidelines, and all applicable regulatory requirements. A copy of the protocol, informed consent forms, and any other documents given to study participants will be submitted to the ethics committees (EC) of all the institutions involved. Written approval will be obtained for all subsequent amendments to the protocol, informed consent documents, and other study documentation referenced above. The investigator will notify the ECs and DSMB of violations of the protocol and serious adverse events. Ethical approval will be sought from the Ethics Committee of the Faculty of Medicine, Pharmacy, and Dentistry of the University of Science, Techniques, and Technologies of Bamako (Bamako, Mali) and the Research Ethics Committee of the London School of Hygiene & Tropical Medicine (London, UK). No activities will start before approval has been received by both committees.

12.1. Confidentiality

The investigator will ensure that the subject's anonymity is maintained. Participants will not be identified in any publicly released reports of this study. All records will be kept confidential to the extent provided by laws and regulations. The study monitors and other authorized representatives of the regulatory authorities may inspect all documents and records required to be maintained by the Investigator.

All laboratory specimens, evaluation forms, reports, and other records that leave the site will be identified only by a coded number to maintain subject confidentiality.

Fully anonymized data will be uploaded to publicly available data repositories (e.g. <https://datadryad.org/>, <https://www.biorxiv.org/>) if requested as a pre-requisite for publication of this research. This will be explained in the participant information and during the consenting procedure. The upload of anonymized data will only be permitted if the participants/participants parents provide explicit approval during consent (a tick box in addition to the signature required for trial participation).

12.2. Risk

This study only involves the use of antimalarial drugs at doses equal or lower than the recommended dosing and schedules. All drugs have been studied thoroughly and their toxicities are well described.

Venipuncture can be associated with pain and bruising at the site of the prick, and rarely infection. Risks will be minimized by the study sites by ensuring adequate training of staff in all procedures and supply of consumables. The study site adheres to the standards of GCP and will be monitored.

12.2.1. Risk of artesunate-amodiaquine

About 30% of treated patients experience adverse reactions. Most of the reported adverse reactions are similar to symptoms usually seen during a malaria attack. Common side effects of artesunate-amodiaquine include anorexia, abdominal pain, nausea, asthenia, somnolence, insomnia and cough. More serious adverse reactions, although infrequently, are anaemia and vertigo.

12.2.2. Risk of primaquine

Primaquine is known to cause dose-dependent haemolysis among individuals who are deficient in glucose-6-phosphate dehydrogenase (G6PD), an enzyme involved in glucose metabolism prevalent in malaria endemic geographies [31]. Haemolysis in G6PD-deficient individuals is caused by oxidative stress induced by primaquine within red blood cells (RBCs); the extent of haemolysis depends on several factors including the dose of primaquine, the type of G6PD deficiency, the functional G6PD assessment at the time of dosing, the concurrent use of other oxidant drugs, and whether the person is hemizygous (homozygous) or heterozygous for G6PD-deficiency [31]. In 2010 the WHO recommended the addition of a single low dose of primaquine (0.25 mg/kg) to standard ACT treatment, without mandatory G6PD testing to block *P. falciparum* transmission in areas threatened by artemisinin resistance or approaching malaria elimination [1], [32]. The safety of single low dose PQ has subsequently been confirmed in clinical trials where PQ was combined with either DP or AL [33]–[35]; two of these studies were specifically designed to assess safety in G6PD deficient individuals and found no clinically relevant reductions in haemoglobin concentrations [33], [34]. PQ use is now widespread throughout the world, and many countries have adopted the 0.25 mg/kg WHO recommendation for single low dose PQ without prior G6PD testing [36]. Common side effects include heartburn, nausea and abdominal cramps.

12.2.3. Risk of artemether-lumefantrine

Reported AL side effects have generally been mild. The main side effects are GI upset: anorexia (~18%), nausea (~5%), vomiting (~18%), abdominal pain (~5%), and diarrhoea

(~10%), headache (~10%), dizziness (~4%), fatigue (~1%) and sleep disturbance (~2%). Other symptoms reported infrequently include palpitations, myalgia, arthralgia (all of which could be disease related), and rash.

